6.3 PATIENT SETS ANALYSED

Patient sets will be used as defined in the CTP, Section 7.3.

The following table shows which patient set will be used for which class of endpoints.

Table 6.3: 1 Patient sets analysed

Class of endpoint	Patient set	
	RS	TS
Primary and key secondary endpoints		X
Secondary endpoints		X
Further endpoints		X
Safety endpoints		X
Demographic/baseline characteristics		X
Disposition	X	

Note that the number of patients with available data for an endpoint may differ. For details, see [Section 6.6](#).

6.5 POOLING OF CENTRES

This section is not applicable because centre/country is not included in the statistical model.

6.6 HANDLING OF MISSING DATA AND OUTLIERS

In general, the efficacy analyses as well as safety analyses will be evaluated by observed case analysis, i.e. using only available data without imputation.

In efficacy analyses of continuous endpoints, missing data will not be imputed. Depending on the respective endpoint, random coefficient regression or Mixed Model Repeated Measurements (MMRM) will be applied, which both analyse all available information from the observed data, using the within-patient correlation structure to provide information about the unobserved data. This method does not employ explicit imputation to handle missing data.

In the analyses of the binary endpoints, missing data will be imputed using the worst case.

According to (001-MCS-36-472_RD-01) (6), missing biomarker data (NOS - no sample available, NOR - no valid result, NOA - not analysed) will not be imputed.

Handling of data below or above the limit of quantification:

- BLQ data will be replaced by $\frac{1}{2}$ LLOQ
- ALQ data will be replaced by ULOQ, if ULOQs are available. Otherwise, ALQ data will be excluded from the analysis.

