#### Premature withdrawal

Patients who prematurely discontinue study drugs (refer to [Section 3.3.4](#)) before the planned end of treatment at Visit 10, should come to the clinic as soon as possible after last drug intake for an early EOT visit. Reason for discontinuation must be documented in the eCRF. For detailed description of the trial procedures at this visit, please refer to the [Flow Chart](#).

In addition patients will be invited to attend all remaining planned visits and perform all study procedures. If a patient doesn't accept to attend remaining study visits, collect the home spirometer and any trial related supplies and contact patient for vital status collection at week 52. The need to come to remaining scheduled visits in case of prematurely discontinuation of trial medication will be explained to patients prior to their participation in the trial.

Vital status information

In case of an early discontinuation of trial medication, if the patient does not agree to come to future visits as planned, any attempt will be made to get information on vital status at Week 52 (refer to [Flow Chart](#)).

Patients will be asked to agree to be contacted by the site personnel, which could be by telephone calls, to allow collection of this information.

If death occurs, the investigator will review the circumstances, including the relevant medical records to ascertain the most likely primary and secondary causes of death.

Collection of vital status will be performed in accordance with national ethical and regulatory guidelines. The need for vital status information will be explained to patients prior to their participation in the trial.

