### **7.3.1 Primary endpoint analyses**

The primary endpoint is the rate of change (slope) in blood CRPM evaluated from baseline over 12 weeks (expressed in ng/mL/month) estimated from measurements taken over 12 weeks of treatment. The rate of change (slope) in blood CRPM is assumed to be linear within each subject over the 12 weeks period. The intercepts and slopes will be assumed to be normally distributed with arbitrary covariance matrix. Gender, age and height which are usual predictors of FVC will also be included in the model. Baseline blood CRPM will be measured at visit 2. No imputation is planned if this assessment is not available for a patient. The within patient error will be assumed to be independent and normally distributed with mean zero and a common variance. The Kenward-Roger approximation will be used to estimate denominators degrees of freedom. Significance tests will be based on least-squares means using a two-sided  $\alpha=0.05$  (two-sided 95% confidence intervals). Analyses will be implemented using SAS® Version 9.4.

The linearity assumption for the rate of change (slope) in blood CRPM will be tested and sensitivity analysis will be done with alternative models described in the Trial Statistical Analysis Plan (TSAP). The effect of missing data will be investigated using pattern-mixture models. Depending on the pattern of the missingness in the data, multiple imputation methods may also be considered.

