## **7.5 HANDLING OF MISSING DATA**

### **7.5.1 Efficacy endpoints**

In efficacy analyses of continuous endpoints, missing data will not be imputed. In the analyses of the time-to-event endpoints, missing or incomplete data are managed by standard survival analysis techniques. These will be described in detail in the TSAP.

In the analyses of the categorical endpoints, missing data will be imputed using the worst case.

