5.2.1 Key secondary endpoint(s)

The key secondary endpoint is the proportion of patients with disease progression as defined by absolute FVC (% predicted) decline $\geq 10\%$ or death until week 52 based on in clinic supervised spirometry.

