 - last trial drug intake plus 29 days
 - date of trial completion
 - follow-up visit
 - early end of treatment visit plus 1 day to database lock

^[a] In addition, a post-treatment period of 7 days will be used for adverse event analyses to more closely reflect the period of time after the last trial drug intake when measurable drug levels or pharmacodynamic effects are still likely to be present.

In addition to the above periods, the following additional period is defined:

- Overall: Combines all available data from Blinded treatment period and Open-label treatment period.

For safety analyses, data up to the end of the blinded / open-label post-treatment period will be considered on-treatment. For on-treatment efficacy analyses, data up to the day after last trial drug intake (included) will be considered.

For efficacy analyses patients will be assigned to the treatment group they were randomised to, for safety analyses patients will be assigned to the treatment group they were treated in.

Details are provided in [Table 6.1: 1](#).

Table 6.1: 1 Summary of analysed periods according to the type of endpoint

Analysed endpoint	Studied period	
	Start date	End date ^{1/1}
For primary analysis (rate of change (slope) in blood CRPM from baseline to week 12)	Baseline (see Section 6.7)	Visit 5 (after time windowing, refer to Section 6.7) Data up to the day after last blinded trial drug intake (included).
For the key secondary endpoint (Proportion of patients with disease progression as defined by absolute FVC (% predicted) decline $\geq 10\%$ or death until week 52)	Main analysis: Baseline (see Section 6.7) Sensitivity analysis: Visit 5 (start of open label treatment)	Visit 10 (after time windowing, refer to Section 6.7) Data up to the day after last open-label trial drug intake (included).
For secondary endpoints (rate of change (slope) in blood C1M and C3M from baseline to week 12)	Baseline (see Section 6.7)	Visit 5 (after time windowing, refer to Section 6.7) Data up to the day after last blinded trial drug intake (included).
For efficacy endpoints from week 12 to week 52 (open-label period)	Visit 5 (start of open label treatment) Note: Covariates can be measured before Visit 5.	Visit 10 (after time windowing, refer to Section 6.7) Data up to the day after last trial open-label drug intake (included).

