7.5 SECONDARY ENDPOINT(S)

7.5.1 Key secondary endpoint(s)

The key secondary endpoint is defined as the proportion of patients with disease progression as defined by absolute FVC (% predicted) decline $\geq 10\%$ or death until week 52.

The following analyses are planned:

- Firstly, in order to assess the association of change in extracellular matrix (ECM) biomarker CRPM over 12 weeks with disease progression as defined by FVC decline $\geq 10\%$ or death over 52 weeks, a logistic regression analysis including baseline blood

CRPM and the rate of change (slope) in blood CRPM over the first 12 weeks as covariates will be applied **for the placebo treated patients only**.

By doing this, the potential of CRPM as a prognostic biomarker is evaluated.

- Secondly, in order to assess how Nintedanib treatment during the first 12 weeks affects the association between change in extracellular matrix (ECM) biomarker CRPM over 12 weeks and disease progression, a logistic regression analysis including baseline blood CRPM, rate of change (slope) in blood CRPM over the first 12 weeks, treatment and treatment CRPM slope interaction as covariates will be applied. **The interaction term will be of primary interest within this analysis.**
- Thirdly, in order to assess whether the overall treatment regimen affects disease progression as defined by FVC decline $\geq 10\%$ or death over 52 weeks, a logistic regression analysis including baseline blood CRPM and randomized treatment as covariates will be applied. **The treatment effect will be of primary interest within this analysis.**
- Fourthly, in order to assess whether rate of change (slope) in blood CRPM over the first 12 weeks to some extent explains the effect of treatment regimen on disease progression as defined by FVC decline $\geq 10\%$ or death over 52 weeks, a logistic regression analysis including baseline blood CRPM, rate of change (slope) in blood CRPM over the first 12 weeks and randomized treatment as covariates will be applied. **The treatment effect will be of primary interest within this analysis.**

Patients who died or progressed in the blinded phase are not at risk in the open label period, but will be considered in the main analysis (including their progression and/or death).

The four main analyses of the key secondary endpoint outlined at the beginning of this section will be repeated by replacing CRPM by C1M and C3M, respectively.

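### Worst-case imputation of progression has no assured conservative direction in the placebo-only CRPM analysis, and the key secondary data cut conflicts with an endpoint that runs to week 52

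*SAP*

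**What the plan says.** **Missing outcomes.** SAP 6.6 starts from a general rule: "In general, the efficacy analyses as well as safety analyses will be evaluated by observed case analysis". It then makes an exception: "In the analyses of the binary endpoints, missing data will be imputed using the worst case". Protocol 7.5.1 agrees: "In the analyses of the categorical endpoints, missing data will be imputed using the worst case". Neither document defines the worst case.

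**The analysis affected.** SAP 7.5.1 gives the purpose of its first analysis: "in order to assess the association of change in extracellular matrix (ECM) biomarker CRPM over 12 weeks with disease progression". This is a logistic regression on baseline CRPM and CRPM slope, restricted to the placebo arm and intended to judge CRPM as a prognostic marker. Three further logistic analyses follow, and all four are repeated for C1M and C3M.

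**The endpoint and its data.** SAP 5.2.1 defines progression as an absolute fall in FVC % predicted of at least 10% "or death until week 52 based on in clinic supervised spirometry". SAP Table 6.1:1 gives the end of the data period for this endpoint as Visit 10 and adds: "Data up to the day after last open-label trial drug intake (included". Protocol 6.2.3 says of patients who stop drug early: "In addition patients will be invited to attend all remaining planned visits and perform all study procedures". For those who decline, it seeks vital status at week 52.

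**Multiple imputation.** Protocol 7.3.1 allows for it, for the primary endpoint: "Depending on the pattern of the missingness in the data, multiple imputation methods may also be considered".

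**The concern.** In a comparison of treatment with control, counting missing patients as failures at least has a recognisable intent. In a regression within one arm there is no treatment to disadvantage. The rule adds assumed events to each part of the CRPM slope range in proportion to how many patients are missing there. The estimated odds ratio then partly reflects who left, and the sign of the error depends on a pattern that is not known when the plan is written.

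This matters because the placebo-only analysis drove the sample size of 350 (protocol 7.7) and is the trial's attempt to confirm the earlier cohort finding (protocol 2.2). The data cut adds to the problem. Read literally, it sets aside FVC and deaths that the protocol works to collect, and it may increase the number of patients to whom the imputation rule applies.

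**Working it through.** **Inputs.** From protocol 7.7: 233 placebo patients, about half with rising CRPM (taken as 116 stable, 117 rising), progression 30% against 50%, two-sided 5% test, stated power 88%, no allowance for withdrawal. Missing rates are assumed throughout.

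**Plan's own figure.** Two-proportion z-test with pooled variance under the null:
- mean rate = (116×0.30 + 117×0.50)/233 = 0.400
- s0 = √[0.400×0.600×(1/116 + 1/117)] = 0.0642
- s1 = √[0.30×0.70/116 + 0.50×0.50/117] = 0.0628
- power = Φ[(0.20 − 1.96×0.0642)/0.0628] = Φ(1.18) = 0.881

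The 88% reproduces. The odds ratio is (0.50/0.50)/(0.30/0.70) = 2.33. Like the protocol's calculation, this dichotomises the slope; the planned model uses the slope itself.

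**Worst-case rule.** If a fraction m of a slope group is missing and a fraction q of those truly progress, the analysed rate is p* = p + m(1 − q). If missingness is unrelated to outcome within the group, q = p.

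*Missingness unrelated to slope and outcome*

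| Missing | Analysed rates, stable / rising | OR | Power | Observed-case power (OR 2.33) |
|---|---|---|---|---|
| 5% | 33.5% / 52.5% | 2.19 | 84% | 86% |
| 10% | 37% / 55% | 2.08 | 79% | 84–85% |
| 20% | 44% / 60% | 1.91 | 69% | 80% |

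*Missingness differing by slope, q = p*
- Rising 15%, stable 5%: 0.50 + 0.15×0.50 = 0.575 against 0.30 + 0.05×0.70 = 0.335, OR 2.69 (inflated).
- Rising 5%, stable 15%: 0.525 against 0.405, OR 1.62, power 45% (shrunk).
- No true association (40% in both), rising 15%, stable 5%: 0.49 against 0.43, OR 1.27, rejection 15%. With 15% and 10%: OR 1.13, rejection 7.4%.

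*Missing patients mostly progress, q = 0.70 with overall rates held fixed*
- 10% missing in both groups: worst case 0.33 against 0.53, OR 2.29. Observed cases alone: (0.30 − 0.07)/0.90 = 0.256 against (0.50 − 0.07)/0.90 = 0.478, OR 2.67. Here worst case is the less biased.
- No association, rising 15%, stable 5%: 0.445 against 0.415, rejection 7.5%, not 15%.
- True association, rising 5%, stable 15%: 0.515 against 0.345, OR 2.02, power 75%, not 45%.

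**Multiple imputation from FVC.** The arm was simulated with continuous CRPM slope, FVC at the eight post-baseline visits, 4% known deaths, and earlier observed progression retained. Variances, death rate and dropout mechanisms were assumed. At 20% dropout, against a true log odds ratio of 0.533 per SD of slope:

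| Dropout | Worst-case bias | MI bias |
|---|---|---|
| unrelated to slope | −0.124 | +0.005 |
| rising with slope | +0.190 | +0.013 |
| falling with slope | −0.430 | +0.001 |

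With no association and slope-related dropout, type I error was 55–57% for worst case and 2–4% for MI. Across 56 scenarios MI had an RMSE lower by more than 0.005 in 32. With no association and dropout unrelated to slope, the two methods performed about equally.

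MI can also do worse. In a second simulation (status at week 52 only, no deaths), 70% of missing patients progressed for reasons not in their observed FVC:

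| Missing | Full-data OR | Worst-case OR | MI OR | Observed-case OR |
|---|---|---|---|---|
| 10% | 2.38 | 2.33 | 2.56 | 2.71 |
| 20% | 2.32 | 2.25 | 2.75 | 3.25 |

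MI put progression at 38% and 36% against a true 40%.

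**Data cut.** Set beside SAP 5.2.1 and protocol 6.2.3, the end date in Table 6.1:1 leaves open whether a patient who stops drug at, say, week 24 is classified on FVC to week 24 or treated as missing. Either way, later clinic FVC and a later death may go unused.

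**The case against.** The worst-case rule is pre-specified and identical in both documents, so it is a choice and not an inconsistency. It is close to correct if patients who disappear have mostly progressed, which is plausible in this disease. The largest distortions above need missingness that differs threefold by CRPM slope and missing patients who progress no more often than others; the documents support neither. Samples are shipped in batches and analysed later (protocol 5.5), so nothing suggests that CRPM results drive withdrawal. All of this stands, and it limits the size of the claim.

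The SAP shown is also incomplete. Table 6.1:1 lists a sensitivity analysis starting at Visit 5 that the visible 7.5.1 does not describe. Footnote 1 to the end date is not shown. The reference list contains a multiple-imputation text that no visible section cites. A reader might infer that the plan has no alternative to worst case; the documents do not support that.

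A reader might also infer that MI should replace worst case as the main analysis. The simulations do not establish this: the preference depends on the mix of scenarios, and MI is the more biased method where missing patients progress for reasons their observed FVC does not show.

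On the data cut, SAP 6.1 deliberately defines on-treatment efficacy data this way. That explains the cut but does not reconcile it with an endpoint running to week 52.

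**Conclusion.** The concern holds in two limited parts.

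First, worst-case imputation has no guaranteed conservative direction in the placebo-only analysis. At an assumed 10% missing, unrelated to slope and outcome, it costs about 9 points of power (88% to 79%) and moves the odds ratio from 2.33 to 2.08. With assumed 15% and 5% missing by slope group, the odds ratio ranges from 1.62 to 2.69, and a null association is rejected 15% of the time. These errors shrink if missing patients mostly progress; the null rejection falls to 7.5% at q = 0.70. Observed-case analysis is no safe default either, since it is then biased upward.

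Second, the data cut in Table 6.1:1 is not reconciled with the endpoint or with the follow-up the protocol collects. This part needs no assumed rate, though footnote 1 might qualify it.

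The 88% power figure is not in error. It assumes complete outcomes.

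**What to change.** 1. **Settle the data first.** Reconcile Table 6.1:1 with the endpoint so that observed clinic FVC and known deaths to week 52 count whether or not drug was stopped. If the on-treatment basis is kept, do this at least in a stated sensitivity analysis. Say when progression status counts as missing, and define the worst case.
2. **Add multiple imputation.** For the key secondary logistic analyses, pre-specify imputation of missing clinic FVC from each patient's longitudinal FVC, CRPM slope and baseline CRPM (the corresponding marker for C1M and C3M). Use known deaths, derive progression from the imputed values and combine by Rubin's rules. Report it beside worst-case and observed-case results, and require the CRPM conclusion to be read across all three. Making it the main analysis is optional; if that is done, record the departure from protocol 7.5.1 in SAP section 4, which now lists no changes.
3. **Cross-refer.** If SAP text not shown already does this, point to it from 6.6 and 7.5.1.

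The cost is SAP wording and modest programming, with no new data collection. The MI analysis rests on a missing-at-random assumption, which the retained worst-case analysis helps to probe.

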5.1 PRIMARY ENDPOINT

The primary endpoint is the rate of change (slope) in blood CRPM from baseline to week 12.

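### When no ULOQ is available, SAP 6.6 deletes biomarker values because they are high; the observed-data slope model does not correct for this

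*SAP*

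**What the plan says.** SAP 6.6 treats the two ends of the assay range differently. At the lower end every value is kept: "BLQ data will be replaced by" half the LLOQ. At the upper end, "ALQ data will be replaced by ULOQ, if ULOQs are available". The next sentence covers the remaining case: "Otherwise, ALQ data will be excluded from the analysis".

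The rule reaches the primary endpoint, since "The primary endpoint is the rate of change (slope) in blood CRPM from baseline to week 12" (SAP 5.1). It also reaches the C1M and C3M slopes (SAP 5.2.2) and the slope covariates in the logistic models of SAP 7.5.1.

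Continuous endpoints are not imputed. SAP 6.6 says that "random coefficient regression or Mixed Model Repeated Measurements (MMRM) will be applied, which both analyse all available information from the observed data". For the primary model, Protocol 7.3.1 adds: "The intercepts and slopes will be assumed to be normally distributed with arbitrary covariance matrix". On missing data the same section says: "The effect of missing data will be investigated using pattern-mixture models". SAP 6.6 lists the missing-biomarker codes as no sample, no valid result and not analysed. Values above the limit are not among them.

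**The concern.** A mixed model fitted to the observed data gives valid slopes if the chance that a value is missing depends only on values that were observed. Here a value is removed exactly when it exceeds a limit, so its absence depends on the value itself. The patient's other visits cannot fully supply what was lost.

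The leverage is considerable because the blinded period has only four sampling times. In a patient whose biomarker rises, the value most likely to be removed is the last one. At stake are the primary slope comparison, the two secondary slope comparisons, and the slope covariate used to judge CRPM as a predictor of progression.

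**Working it through.** **Inputs from the documents.** Sampling at weeks 0, 4, 8 and 12 (Protocol 6.1). Random intercepts and slopes on observed data (Protocol 7.3.1, SAP 6.6). 117 nintedanib and 233 placebo patients, two-sided 5% level, 20% difference, SD of relative change 30%, 40% or 50% (Protocol 7.7).

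**Assumed, because the documents give no figure.** Share of values above the limit 1% to 20%; normal or log-normal values; baseline SD about 35%; SD of the week-12 change about 28% to 54%; mean changes over 12 weeks from -30 to +20 points.

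**Step 1: the plan's own figures.** None is given for this rule, so the nearest is Table 7.7:2. By normal approximation, n(nintedanib) = 1.5 × (1.960 + 1.282)² × (SD/20)² = 1.5 × 10.51 × (SD/20)², with twice as many on placebo:

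- SD 30%: 35.5, so 36 + 71 = 107
- SD 40%: 63.1, so 64 + 127 = 191
- SD 50%: 98.5, so 99 + 198 = 297

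The noncentral t calculation gives 110, 192 and 299, exactly as in the table.

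**Step 2: effect on single slopes.** Simulated data (60,000 patients per scenario), fitted with random intercepts and slopes, 10% of values above the limit and excluded. Slopes are per month.

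| True pattern | All values | After exclusion |
|---|---|---|
| Rising | 3.59 | 1.90 |
| Flat | 0.02 | -1.24 |
| Falling | -3.74 | -4.37 |
| Steeply falling, small slope variance | -10.80 | -9.74 |

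The usual shift is downward, because varying slopes put more values above the limit at late visits. Only the last row moves up.

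**Step 3: effect on the treatment difference, equal spread.** The fraction of the true difference that remains, from simulations with log-normal values and the share taken over all values:

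| Share above limit | Excluded | Loss | Kept at the limit | Loss |
|---|---|---|---|---|
| about 1% | 0.90 | 10% | 0.94 | 6% |
| about 2% | 0.85 | 15% | 0.90 | 10% |
| about 4% | 0.80 | 20% | 0.85 | 15% |
| about 8% | 0.70 | 30% | 0.75 | 25% |

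A separate set of simulations gave, for exclusion, 0.91 to 0.94 at 1% and 0.76 to 0.82 at 5% with log-normal values. With normal values it gave 0.96 to 0.98 and 0.89 to 0.93. A true zero difference stayed near zero.

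**Step 4: unequal spread.** 10% of values above the limit and excluded; SD of the week-12 change about 28 in one arm and 38 to 39 in the other. Differences are nintedanib minus placebo, per month.

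| True 12-week change (placebo / nintedanib) | Wider arm | All values | After exclusion |
|---|---|---|---|
| 0 / 0 | placebo | 0.10 | 1.15 |
| 0 / 0 | nintedanib | -0.07 | -1.21 |
| 0 / -5 | placebo | -1.85 | -0.56 |
| 0 / -5 | nintedanib | -1.82 | -2.58 |
| 0 / -20 | placebo | -7.21 | -5.38 |
| 0 / -20 | nintedanib | -7.12 | -7.28 |

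Unequal spread is plausible. For CRPM, Table 7.7:1 shows 40% on placebo against 25% on treatment (Study B, week 4) and 43% against 47% (Study B, week 12), so either arm can be the wider one.

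**Step 5: power for a diluted difference.** Power = Φ(r × 20 / (SD × √(1/117 + 1/233)) − 1.960), where r is the fraction remaining. At SD 50% the standard error is 50 × 0.1133 = 5.67; for r = 0.80, 16/5.67 − 1.960 = 0.86, so power is 80.6%.

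| r | SD 40% | SD 50% |
|---|---|---|
| 1.00 | 99.3% | 94.2% |
| 0.90 | 97.8% | 88.8% |
| 0.85 | 96.3% | 85.1% |
| 0.80 | 94.2% | 80.6% |
| 0.70 | 87.1% | 69.5% |

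This ignores any change in the standard error and is approximate.

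**The case against.** The strongest objection is that the fallback may never be used. A laboratory can call a result too high only against some limit. If that limit counts as a ULOQ, the first clause applies and nothing is deleted. Protocol 5.5.1 leaves assay methods to a separate report, so the documents do not show that the exclusion would ever be triggered for CRPM, C1M or C3M. This stands as a limit on size. It does not defend the rule: if a limit always exists the sentence serves no purpose, and if it is used it biases the slopes.

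Second, the protocol plans pattern-mixture models and possibly multiple imputation. Nothing in the available text applies them to values above the limit. SAP text between 7.4.1 and 7.5 appears to be absent from the public copy, however, so such an analysis cannot be ruled out.

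Third, replacing a value by the limit is also biased. That is correct: Step 3 shows 6% to 25% loss, and in one 10% case the fraction remaining was about 0.89 when capped against 0.84 when excluded. Capping is better, but only a partial remedy.

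Two stronger readings are tempting. A reader might infer that the rule always pulls slopes toward no change and arms toward no difference. Steps 2 and 4 contradict this: a flat slope turns negative, a falling one can steepen, and with unequal spread a null difference can move away from zero. A reader might also infer that the key secondary analysis misclassifies rising patients. Protocol 2.3 and 3.2 describe a rising versus stable split, and 7.7 bases its power on it. But the models in Protocol 7.3.2 and SAP 7.5.1 enter the slope itself, so the supported statement is that a covariate is distorted.

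**Conclusion.** The point holds in a limited form. Whenever the fallback is used, it removes observations because they are high, and the planned model does not correct this. The slopes are distorted, usually downward. With similar spread in the arms the treatment difference is usually diluted; with unequal spread it may shrink, grow or appear where there is none.

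The size cannot be fixed from the documents and is zero if no value exceeds the limit. The estimate of roughly 10% to 30% loss for about 1% to 8% of all values excluded rests on assumed log-normal values and equal spread. With values closer to normal the loss is smaller, about 2% to 4% at a 1% share. If the SD is 40% or less, the planned 350 patients absorb a 20% loss with power still near 94%; at SD 50% power falls to about 81%. This is a minor point, worth correcting because the correction is cheap.

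**What to change.** Before unblinding, replace the fallback sentence in SAP 6.6 with:

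> If no ULOQ is available, ALQ results are kept and set to the limit against which the laboratory reported them as above (the highest reportable value). A sensitivity analysis treats all ALQ results as right-censored in the random-coefficient model. ALQ counts are reported by arm and visit.

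If ULOQs exist for CRPM, C1M and C3M, state them in the SAP and delete the fallback; the censored analysis and the counts remain useful.

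The cost is one SAP sentence, little programming for the cap and the counts, and one additional model. Capping still leaves some attenuation. The limit may also vary between assay runs, since samples are shipped in batches (Protocol 5.5). The censored analysis is there for both reasons.
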